5.7 Criteria to Resume Treatment

Management of adverse events is summarized in section 6 and may include holding of nivolumab and ipilimumab, and/or the use of steroids for the management of immune related AEs.

If drug administration is held until the next scheduled time point, please continue to count weeks/doses. If patients must be delayed due to toxicity, all assessments can be obtained with the modified treatment dose schedule as noted in this section.

Some patients may continue to benefit from treatment, maintaining or improving responses after progression including those treated with steroids.

Restarting nivolumab may be considered in patients who experience grade 2 events and some grade 3 events (skin rash and thyroiditis). Because of this, stopping treatment and starting steroids earlier, as per section 6, to obtain resolution with the possibility for restarting rather than waiting for higher grade events is encouraged.

For non-autoimmune or non-inflammatory events patients may resume treatment with study drug when the drug-related AE(s) resolve to Grade ≤ 1 or baseline value, with the following exceptions:

- Evaluation to exclude any additional immune mediated events endocrine, GI, and liver / pancreas function as clinically indicated must be made prior to restarting.
- Non-drug-related toxicity including hepatic, pulmonary toxicity, diarrhea, or colitis, must have resolved to baseline before treatment is resumed.

If the criteria to resume treatment are met, the patient should restart treatment no sooner than the next scheduled time point per protocol. However, if the treatment is delayed past the next scheduled time point per protocol the treatment should resume at the earliest convenient point that is within the six week delay period.

For protocols using combination nivolumab/Ipilimumab for the initial induction period patients with grade 2 or 3 events requiring discontinuation of treatment with the combination, the PI may consider continuing treatment with single agent nivolumab at the same dose when the event resolves to baseline. However, patients with renal, CNS, or pulmonary toxicity must be removed from study.

For patients treated with corticosteroids:

For patients treated with high dose steroids with nivolumab/Ipilimumab, toxicity must resolve to baseline within 8 weeks of treatment.

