6 DOSING DELAYS/DOSE MODIFICATIONS

Dose delays for nivolumab and ipilimumab for adverse events are described below. There are no dose reductions of nivolumab or ipilimumab allowed. See section 5.6 for guidelines regarding resumption of nivolumab and ipilimumab following dose delays.

Please refer to the Nivolumab Investigator Brochure, Ipilimumab Investigator Brochure or Appendix B to the protocol for toxicity management algorithms which include specific treatment guidelines. These algorithms should be followed unless there are specific clinical circumstances which the treating physician indicates variations or alternative treatment is needed.

Evaluation of possible AEs should occur early, with early withholding of drug, and appropriate treatment as indicated in the management tables and following event specific guidelines. In some cases, nivolumab and ipilimumab may be resumed as per section 5.6

| ALL OTHER EVENTS* | Management/Next Dose for Nivolumab and combination Nivolumab/ipilimumab |
|---------------------------------|--|
| ≤ Grade 1 | No change in dose |
| Grade 2 | Hold until ≤ Grade 1 OR baseline (exceptions as noted below); Evaluate and continue at investigator discretion |
| Grade 3 | Off protocol therapy (exceptions as noted below) |
| Grade 4 | Off protocol therapy |

* **Not agent related**, or agent related non-immunologically mediated

Recommended management: As clinically indicated

| ALL OTHER EVENTS** | Management/Next Dose for Nivolumab and combination Nivolumab/ipilimumab |
|----------------------------------|---|
| ≤ Grade 1 | No change in dose |
| Grade 2 | Hold until ≤ Grade 1 OR baseline* When resolved < or following steroids resume at same dose level . |
| Grade 3 | Off protocol therapy (exceptions noted in 5.4) |

| ALL OTHER EVENTS* | Management/Next Dose for Nivolumab and combination Nivolumab/ipilimumab |
|---|--|
| Grade 4 | Off protocol therapy |
| ** immunologically mediated | |
| Recommended management: As clinically indicated | |

- Any grade 2 drug-related uveitis or eye pain or blurred vision that does not respond to topical therapy and does not improve to Grade 1 severity within the re-treatment period OR requires systemic treatment should go off protocol treatment.
- Any adverse event, laboratory abnormality, or intercurrent illness which, in the judgment of the investigator, presents a substantial clinical risk to the subject with continued study drug dosing should go off protocol treatment.

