- Tumor pain or associated tumor flare does not require permanent discontinuation.
- Any grade < 2 laboratory only abnormality may continue study treatment at the discretion of the investigator. Any grade 3 or 4 drug-related laboratory abnormality or electrolyte abnormality, that can be managed independently from underlying organ pathology with electrolyte replacement, hormone replacement, insulin, or that does not require treatment **does not** require discontinuation.

| Skin Rash and Oral Lesions | Management/Next Dose for Nivolumab and combination Nivolumab/ipilimumab |
|--|--|
| ≤ Grade 1 | No change in dose;* evaluate and continue at investigator discretion |
| Grade 2 | Hold* until 1≤ Grade resolved^. Evaluate and continue at investigator discretion. |
| Grade 3 | Hold* until ≤ Grade 1; evaluate and resume at investigator discretion same dose level. |
| Grade 4 | Off protocol therapy |

*Patients with purpuric or bullous lesions must be evaluated for vasculitis, Steven-Johnson syndrome, TEN, and autoimmune bullous disease including oral lesions of bullous pemphigus/pemphagoid. Pruritus may occur with or without skin rash and should be treated symptomatically if there is no associated liver or GI toxicity. Note skin rash typically occurs early and may be followed by additional events particularly during steroids tapering.

Recommended management: AE management guidelines – Appendix B

| Liver Function AST, ALT, and Bilirubin (total) | Management/Next Dose for Nivolumab and combination Nivolumab/ipilimumab |
|--|---|
| ≤ Grade 1 | Hold pending evaluation. Continue treatment at same level at investigator decision. |
| Grade 2 | Hold until UNL or baseline. Evaluate and resume at investigator discretion same dose level. |
| Grade 3 | Off protocol therapy |
| Grade 4 | Off protocol therapy |

Continued treatment of active immune mediated hepatitis may exacerbate ongoing inflammation. Holding drug to evaluate LFT changes and early treatment are recommended.

| Liver Function AST, ALT, and Bilirubin (total) | Management/Next Dose for Nivolumab and combination Nivolumab/ipilimumab |
|---|--|
| LFT changes may occur during steroid tapers from other events and may occur together with other GI events including cholecystitis/pancreatitis. | |
| Recommended management: see Hepatic AE management algorithm | |

| Diarrhea/ Colitis | Management/Next Dose for Nivolumab and combination Nivolumab/ipilimumab |
|--|---|

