| ≤ Grade 1 | Asymptomatic TSH elevation*; continue at investigator discretion with evaluation of thyroid function. |
| Grade 2 | Hold until patients are on a stable replacement hormone regimen. If treated with steroids, patients must be stable off steroids for two weeks. Resume at same dose level. |
| Grade 3 | Off protocol therapy. |
| Grade 4 | Off protocol therapy |
| 
Note all patients with symptomatic pituitary enlargement, exclusive of hormone deficiency, but including severe headache or enlarged pituitary on MRI should be considered grade 3 events. Isolated thyroid or testosterone deficiency may be treated as grade 2 if there are no other associated deficiencies and adrenal function is monitored.
 
Please evaluate pituitary function before beginning steroid therapy or replacement therapy of any kind.
 
*Note patients with thyroiditis may be retreated on replacement therapy. Patients must be evaluated to rule out pituitary disease prior to initiating thyroid replacement.
 | |
| 
Recommended management: TSH, T3, and T4 will be collected at baseline. After baseline, TSH will be collected every 6 weeks; T3/T4 will be collected when indicated. See Endocrine Management Algorithm
 | |

| Renal | Management/Next Dose for Nivolumab and combination Nivolumab/ipilimumab |
|--|--|
| ≤ Grade 1 | Continue at same dose at investigator discretion |
| Grade 2 | Hold pending evaluation. Resume at same dose level at investigator discretion. |
| Grade 3 | Off study treatment |
| Grade 4 | Off study treatment |
| 
Patients with fever should be evaluated as clinically appropriate. Patients may experience isolated fever during infusion reactions or up to several days after infusion. Evaluation over the course of 1-2 weeks should be done for other autoimmune events that may present as fever
 | |
| Infusion reaction | Management/Next Dose for Nivolumab and combination Nivolumab/ipilimumab |
| ≤ Grade 1 | Continue at slower rate at investigator discretion |
| Grade 2 | Hold until ≤ Grade 1. Resume at same dose level |
| Grade 3 | Hold until ≤ Grade 1. Resume at same dose level |
| Grade 4 | Off protocol therapy |

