APPENDIX A PERFORMANCE STATUS CRITERIA

| ECOG Performance Status Scale | | Karnofsky Performance Scale | |
|-------------------------------|---|-----------------------------|--|
| Grade | Descriptions | Percent | Description |
| 0 | Normal activity. Fully active, able to carry on all pre-disease performance without restriction. | 100 | Normal, no complaints, no evidence of disease. |
| | | 90 | Able to carry on normal activity; minor signs or symptoms of disease. |
| 1 | Symptoms, but ambulatory. Restricted in physically strenuous activity, but ambulatory and able to carry out work of a light or sedentary nature (e.g., light housework, office work). | 80 | Normal activity with effort; some signs or symptoms of disease. |
| | | 70 | Cares for self, unable to carry on normal activity or to do active work. |
| 2 | In bed <50% of the time. Ambulatory and capable of all self-care, but unable to carry out any work activities. Up and about more than 50% of waking hours. | 60 | Requires occasional assistance, but is able to care for most of his/her needs. |
| | | 50 | Requires considerable assistance and frequent medical care. |
| 3 | In bed >50% of the time. Capable of only limited self-care, confined to bed or chair more than 50% of waking hours. | 40 | Disabled, requires special care and assistance. |
| | | 30 | Severely disabled, hospitalization indicated. Death not imminent. |
| 4 | 100% bedridden. Completely disabled. Cannot carry on any self-care. Totally confined to bed or chair. | 20 | Very sick, hospitalization indicated. Death not imminent. |
| | | 10 | Moribund, fatal processes progressing rapidly. |
| 5 | Dead. | 0 | Dead. |

**APPENDIX B MANAGEMENT ALGORITHMS FOR ENDOCRINOPATHY,
GASTROINTESTINAL, HEPATIC, NEUROLOGICAL, PULMONARY, RENAL, AND
SKIN ADVERSE EVENTS**

Endocrinopathy Management Algorithm

[figure not shown]
Rule out non-inflammatory causes. If non-inflammatory cause, treat accordingly and continue immuno-oncology (I-O) therapy. Consider visual field testing, endocrinology consultation, and imaging.

Patients on IV steroids may be switched to an equivalent dose of oral corticosteroids (e.g. prednisone) at start of tapering or earlier, once sustained clinical improvement is observed. Lower bioavailability of oral corticosteroids should be taken into account when switching to the equivalent dose of oral corticosteroids.

GI Adverse Event Management Algorithm

[figure not shown]

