Rule out non-inflammatory causes. If non-inflammatory cause is identified, treat accordingly and continue I-O therapy. Opiates/narcotics may mask symptoms of perforation. Infliximab should not be used in cases of perforation or sepsis.

Patients on IV steroids may be switched to an equivalent dose of oral corticosteroids (e.g. prednisone) at start of tapering or earlier, once sustained clinical improvement is observed. Lower bioavailability of oral corticosteroids should be taken into account when switching to the equivalent dose of oral corticosteroids.

Hepatic Adverse Event Management Algorithm

Rule out non-inflammatory causes. If non-inflammatory cause, treat accordingly and continue I-O therapy. Consider imaging for obstruction.

[figure not shown]
Patients on IV steroids may be switched to an equivalent dose of oral corticosteroids (e.g. prednisone) at start of tapering or earlier, once sustained clinical improvement is observed. Lower bioavailability of oral corticosteroids should be taken into account when switching to the equivalent dose of oral corticosteroids.

*I-O therapy may be delayed rather than discontinued if AST/ALT \leq 8 x ULN and T.bili \leq 5 x ULN.

**The recommended starting dose for grade 4 hepatitis is 2 mg/kg/day methylprednisolone IV.

Neurological Adverse Event Management Algorithm

[figure not shown]
Rule out non-inflammatory causes. If non-inflammatory cause, treat accordingly and continue I-O therapy.

Patients on IV steroids may be switched to an equivalent dose of oral corticosteroids (e.g. prednisone) at start of tapering or earlier, once sustained clinical improvement is observed. Lower bioavailability of oral corticosteroids should be taken into account when switching to the equivalent dose of oral corticosteroids.

Pulmonary Adverse Event Management Algorithm

[figure not shown]
Rule out non-inflammatory causes. If non-inflammatory cause, treat accordingly and continue I-O therapy. Evaluate with imaging and pulmonary consultation.

Patients on IV steroids may be switched to an equivalent dose of oral corticosteroids (e.g. prednisone) at start of tapering or earlier, once sustained clinical improvement is observed. Lower bioavailability of oral corticosteroids should be taken into account when switching to the equivalent dose of oral corticosteroids.

Renal Adverse Event Management Algorithm

[figure not shown]
Rule out non-inflammatory causes. If non-inflammatory cause, treat accordingly and continue I-O therapy

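### For a Grade 3 or 4 event with a non-inflammatory cause, Appendix B says to continue immunotherapy while the Section 6 liver, neurologic, endocrine and renal rows stop it, and no text says which governs

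*Combined protocol and SAP*

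**What the plan says.** **Appendix B** holds seven algorithms: endocrine, gastrointestinal, hepatic, neurological, pulmonary, renal and skin. The endocrine one reads "If non-inflammatory cause, treat accordingly and continue immuno-oncology (I-O) therapy", the gastrointestinal one "If non-inflammatory cause is identified, treat accordingly and continue I-O therapy" and the hepatic one "If non-inflammatory cause, treat accordingly and continue I-O therapy. Consider imaging for obstruction". The other four carry the same instruction. A hepatic footnote allows therapy to be delayed instead of discontinued when AST/ALT is at most 8 x ULN and total bilirubin at most 5 x ULN.

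**Section 6** gives the algorithms default standing: "These algorithms should be followed unless there are specific clinical circumstances", the circumstances being left to the treating physician. Its own tables then set the next dose by organ and grade:

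- Liver, neurologic and endocrine: Grades 3 and 4 go off protocol therapy.
- Renal: the Grade 3 and 4 rows read "Off study treatment".
- Liver Grade 2: "Hold until UNL or baseline. Evaluate and resume at investigator discretion same dose level".
- The single-asterisk table for all other events covers those that are not agent related, or agent related but not immune mediated. It stops at Grade 3 (with exceptions) and at Grade 4.

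**Section 5.7** sets conditions for restarting. Its lead rule is "For non-autoimmune or non-inflammatory events patients may resume treatment with study drug when the drug-related AE(s) resolve" to Grade 1 or lower, or to the baseline value. Among the exceptions is "Non-drug-related toxicity including hepatic, pulmonary toxicity, diarrhea, or colitis, must have resolved to baseline before treatment is resumed".

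**The concern.** A site facing a serious liver, neurologic, endocrine or renal event that proves non-inflammatory finds one text that continues dosing and another that ends it. Both are live instructions, because Section 6 contains the stop rows and also directs sites to Appendix B. The liver table itself points to the hepatic algorithm.

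The first stake is patient safety: whether someone is dosed through an unresolved organ event or permanently stopped should not depend on which page is open. The second is interpretation. Exposure and discontinuation for toxicity would partly reflect how each site read the protocol.

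**Working it through.** The check compares texts; the plan gives no figure to reproduce.

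**Step 1. Lead sentence.** Count of Appendix B algorithms telling sites to continue when the cause is non-inflammatory: 7 of 7. None has a grade limit in its readable text.

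**Step 2. Section 6 against that sentence.**

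| Section 6 table | Grade 3 | Grade 4 | Cause considered in those rows? |
|---|---|---|---|
| Liver | Stop | Stop | No |
| Neurologic | Stop | Stop | No |
| Endocrine | Stop | Stop | No |
| Renal | Stop | Stop | No |
| All other events, non-immune | Stop, with exceptions | Stop | Defined by cause, and still stops |
| Skin | Hold, then resume | Stop | No |
| Diarrhea/colitis | Hold, then resume | Stop | Evaluation of other causes is required |
| Pneumonitis | Hold; resume once agent-associated pneumonitis is excluded | Stop | Yes at Grade 3 |

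The first four tables give 4 organs x 2 grades = 8 rows that say stop where Appendix B says continue. The cardiac table has no Appendix B algorithm to conflict with; for suspected myocarditis it allows resumption once that is excluded or unlikely and the patient is back to baseline.

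**Step 3. Exceptions elsewhere.** Section 6 spares Grade 3-4 drug-related laboratory abnormalities that need no treatment, or that can be managed apart from underlying organ pathology. It also lets Grade 3 thyroiditis be handled as Grade 2. These narrow the endocrine and laboratory-only cases. They do not reach an event with organ pathology, such as the biliary obstruction for which the hepatic algorithm suggests imaging.

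**Step 4. Section 5.7.** It applies once drug has been held. A drug-related, non-inflammatory event must reach Grade 1 or baseline. Non-drug-related hepatic or pulmonary toxicity, diarrhea or colitis must reach baseline. Neither condition matches an unqualified instruction to continue. Renal events are not named in the baseline exception.

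**Step 5. Hepatic footnote.** The liver rows at Grade 2 and below already hold drug. An allowance to delay instead of discontinue can therefore change what Section 6 requires only at Grades 3 or 4, and those rows offer no delay.

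**Step 6. Precedence.** No sentence ranks Appendix B, Section 5.7 and the Section 6 tables. The cross-references do not help. Section 6 sends readers to 5.6 for resumption rules, but 5.6 covers removal from study and resumption is in 5.7. Section 5.4 cites an Appendix E for the algorithms, while the contents list only Appendices A and B.

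**Worked case.** Take a Grade 3 liver event from obstruction. The Appendix B lead sentence says treat and continue; the Section 6 liver row says stop. If drug was held during evaluation, 5.7 would require baseline, or Grade 1 or baseline, depending on drug-relatedness.

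**The case against.** **The flow charts.** The charts for most algorithms could not be read for this check, and the hepatic footnotes suggest boxes for delay and discontinuation by grade. A chart might limit the lead sentence. This stands as a caveat, and anyone with the charts should look there first. It would not by itself reconcile the footnote with the liver rows.

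**Division of labour.** The Section 6 tables have a next-dose column and cite the algorithms as recommended management, which suggests that tables govern dosing and algorithms govern treatment of the event. The lead sentence may also be only a sorting step that sends non-inflammatory events out of the immune pathway. Both readings are reasonable, but neither is stated. The lead sentence itself speaks about dosing, and an event sorted out of the immune pathway meets a non-immune table that stops at Grade 3, subject to its exceptions.

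**Physician judgment.** The discretion clause permits departures from the algorithms. It does not say which text is the default when they differ.

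**Stronger readings to avoid.** A reader might infer that every one of the seven algorithms collides with two other rules, giving three instructions per patient. The documents do not support that. Section 5.7 governs resumption after a hold, not whether to stop, and it sorts by drug-relatedness, which overlaps with non-inflammatory cause but is not the same. Nor do all Section 6 tables ignore cause: pneumonitis and cardiac consider it, and diarrhea/colitis Grade 3 is held and resumed. A reader might also expect a measurable shift in Cohort B's response or 6-month PFS counts. The documents give no number of affected patients, and Section 13.6.2 keeps eligible patients in the response analysis despite incorrect administration.

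**Conclusion.** The contradiction holds in a limited form. For Grade 3 or 4 liver, neurologic, endocrine and renal events with a non-inflammatory cause, the Appendix B lead sentence and eight Section 6 rows give opposite instructions on continuing therapy. The non-immune table in Section 6 also stops, with exceptions. Section 5.7 and the hepatic footnote add smaller mismatches. Diarrhea/colitis, pneumonitis and cardiac events conflict less or not at all.

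This is a rule that cannot be followed as written, so it is more than missing detail. It matters mainly for safety, and no effect on the efficacy counts is claimed. The conclusion assumes that the unseen charts neither restrict the lead sentence by grade nor state a precedence, and that the event falls outside the laboratory and thyroiditis exceptions.

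**What to change.** In the next amendment, reconcile the opening sentence of the Appendix B algorithms and the hepatic delay footnote with Section 5.7 and with the Section 6 stop rows (liver, neurologic, endocrine, renal and the non-immune table). State which text takes precedence for events with a non-inflammatory cause, and whether Section 5.7's drug-related and non-drug-related classes are meant to correspond to that category. Correct the Section 6 pointer to 5.6 and the Section 5.4 pointer to Appendix E at the same time. The clinical rule for each organ and grade is for the sponsor and investigators to decide.

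The cost is protocol wording only, with no added procedures, visits or patients.
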